6.3 Missing Data Imputation

No data will be imputed for any efficacy or safety analyses except for the PRO questionnaires, for analyses of the HCV RNA endpoints, and for analysis of the persistence of resistance. If a respondent answers at least 50% of the items in a multi-item scale of the SF-36v2, the missing items will be imputed with the average score of the answered items in the same scale. In cases where the respondent did not answer at least 50% of the items, the score for that domain will be considered missing. Similarly, the missing items of the FACIT-F questionnaire will be imputed with the average score of the answered items in the same scale as long as more than 50% (≥ 7 out of 13) of the items in the scale are answered. The SF-36v2 Mental and Physical Component Summary measures will not be computed if any domain is missing.

HCV RNA values will be selected for an SVR analysis based on visit windows as defined in Section 6.2. When there is no HCV RNA value in a visit window based on defined visit windows, the closest values before and after the window, regardless of the value chosen for the subsequent and preceding window, will be used for the flanking imputation described below.

If a subject has a missing HCV RNA value at a post-Day 1 visit but with undetectable or unquantifiable HCV RNA levels at both the preceding value and succeeding value, the HCV RNA level will be considered undetectable or unquantifiable, respectively, at this visit for this subject. In addition, if a subject has an unquantifiable HCV RNA level at the preceding value and an undetectable HCV RNA level at the succeeding value, or vice versa, the HCV RNA level will be imputed as unquantifiable at this visit for this subject. For SVR analyses, if there is no value in the appropriate window after flanking imputation but there is an HCV RNA value after the window, then it will be imputed into the SVR window. Subsequent to this flanking and backward imputation, if a subject is missing a value for the visit window associated with the analysis, the subject will be imputed as a visit failure (i.e., not undetectable or unquantifiable).

If a subject starts another treatment for HCV, then all HCV RNA and PRO assessment values for this subject measured on or after the start date of the new HCV treatment will be excluded from analyses. The subject will be considered a failure for summaries of viral response at all time points after the start of the new HCV treatment.

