Breakthrough = confirmed HCV RNA \geq LLOQ after HCV RNA < LLOQ during treatment, or confirmed increase from nadir in HCV RNA (two consecutive HCV RNA measurements > 1 log₁₀ IU/mL above nadir) at any time point during treatment. A single breakthrough value (\geq LLOQ or > 1 log₁₀ IU/mL above nadir) followed by lost to follow-up will be considered a breakthrough (i.e., will not require confirmation).

On-treatment virologic failure = breakthrough or failure to suppress during treatment (all on-treatment values of HCV RNA \geq LLOQ) with at least 6 weeks (defined as study drug duration \geq 36 days) of treatment.

RVR (rapid virologic response) = HCV RNA < LLOQ in the Week 4 window.

EOTR (end of treatment response) = HCV RNA < LLOQ in the Week 12 window for subjects receiving 12 weeks of treatment and in the Week 24 window for subjects receiving 24 weeks of treatment.

SVR₄ = HCV RNA < LLOQ in the SVR₄ window (4 weeks after the last actual dose of study drug) without any confirmed quantifiable (\geq LLOQ) post-treatment value during that SVR window.

SVR₁₂ = HCV RNA < LLOQ in the SVR₁₂ window (12 weeks after the last actual dose of study drug) without any confirmed quantifiable (\geq LLOQ) post-treatment value before or during that SVR window.

SVR₂₄ = HCV RNA < LLOQ in the SVR₂₄ window (24 weeks after the last actual dose of study drug) without any confirmed quantifiable (\geq LLOQ) post-treatment value before or during that SVR window.

Relapse₁₂ = confirmed HCV RNA \geq LLOQ between end of treatment and 12 weeks after last actual dose of active study drug (up to and including the SVR₁₂ assessment time point) for a subject with HCV RNA < LLOQ at Final Treatment Visit who completes treatment.

Relapse₂₄ = confirmed HCV RNA \geq LLOQ during SVR₂₄ window among subjects who achieved SVR₁₂ and have data available during the SVR₂₄ window.

Relapse_{late} = confirmed HCV RNA \geq LLOQ at any time after the SVR₂₄ assessment time point for a subject who achieved SVR₂₄ and has post-SVR₂₄ HCV RNA data available.

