Relapse_{overall} = confirmed HCV RNA \geq LLOQ between end of treatment and up to and including the last HCV RNA measurement collected in the PT Period for a subject with HCV RNA < LLOQ at Final Treatment Visit who completes treatment. For relapse analyses, the completion of treatment is defined as a study drug duration \geq 77 days for subjects assigned to 12 weeks of treatment and \geq 154 days for subjects assigned to 24 weeks of treatment. If the last available post treatment value is \geq LLOQ, then the subject will be considered a relapse (i.e., will not require confirmation). Relapse analyses will exclude subjects who do not have any post-treatment HCV RNA values.

HCV re-infection is defined as confirmed HCV RNA \geq LLOQ after the end of treatment in a subject who had HCV RNA < LLOQ at Final Treatment Visit, along with the post-treatment detection of a different HCV genotype, subtype, or clade compared with baseline, as determined by phylogenetic analysis of the NS3 or NS5A, and/or NS5B gene sequences. Re-infection in the case of the same HCV subtype is defined as a clade

switch, as indicated by the lack of clustering between the baseline and post-treatment sequences by phylogenetic analysis. If phylogenetic analysis is not possible due to technical difficulties, HCV re-infection may be determined with a confirmed HCV genotype or subgenotype switch by the Versant HCV Genotype Inno-LiPA Assay v2.0 or Sanger assay.

Any subjects with documented re-infection will be excluded from relapse analyses and will be analyzed separately.

Reasons for SVR₁₂ Non-Response

Subjects who do not achieve SVR₁₂ (SVR₁₂ non-responders) will be categorized as having:

1. On-treatment virologic failure (see **On-treatment virologic failure** definition);
2. Relapse (defined according to the **Relapse₁₂** definition for subjects who complete treatment);
3. Prematurely discontinued study drug with no on-treatment virologic failure (defined as any SVR₁₂ non-responder who prematurely discontinued study drug (duration < 77 days for subjects assigned to 12 weeks of treatment or duration < 154 days for subjects assigned to 24 weeks of treatment) and did not meet the **On-treatment virologic failure** definition);
4. Missing follow-up data in the SVR₁₂ window [defined as any subject who completed study drug without data in the SVR₁₂ window and not meeting the definitions of (1), (2), or (3)];

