10.6 Sensitivity Analysis for the Efficacy Endpoint of SVR₁₂

In addition to presenting the secondary efficacy endpoint of SVR₁₂ as described in Section 10.4, two sensitivity analyses of SVR₁₂ will be presented using the following modified populations. The first sensitivity analysis of SVR₁₂ will be conducted using a Modified Intention-to-Treat Genotype (mITT-I-GT) population that includes subjects who receive at least 1 dose of study drug in Study M14-423 (with imputation as described in Section 6.3) but excludes the subjects who are not of HCV genotype 1 infection. The mITT-I-GT population is used to reduce the risk of bias that could occur due to enrolled population deviating from the protocol selected study population.

The other sensitivity analysis of SVR₁₂ will be conducted using a Modified Intention-to-Treat Genotype and Virologic Failure (mITT-I-GT+VF) population. The mITT-I-GT+VF population is used to reduce the risk of bias that could occur due to either discordant HCV genotype or irrelevant failures unrelated to study drug. The mITT-I-GT+VF population includes all subjects who receive at least 1 dose of study drug in Study M14-423 (with imputation as described in Section 6.3) but excludes the subjects who are not of HCV genotype 1 infection and the subjects who did not achieve SVR₁₂ due to reasons other than on treatment virologic failure or relapse.

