10.7 Additional Efficacy Analyses

The following additional HCV RNA efficacy endpoints will be summarized and analyzed on the ITT-I population, as specified:

- The number and percentage of subjects with on-treatment virologic failure;
- The number and percentage of subjects with post-treatment relapse;
- The number and percentage of subjects with documented re-infection;
- The number and percentage of subjects with RVR;
- The number and percentage of subject with EOTR;
- The number and percentage with unquantifiable HCV RNA at each post-baseline visit throughout the Treatment Period (using data from the central laboratory as observed, i.e., no imputation for missing data);
- The number and percentage of subjects with HCV RNA < LLOQ 24 weeks after the last actual dose of study drug (SVR₂₄);
- Reasons for not achieving SVR₂₄ for subjects who do not;
- Mean change from baseline in prothrombin time (PT), International normalized ratio (INR), FibroTest, and albumin to each applicable post-baseline time point;
- The number of subjects who fail to suppress and accompanying listing;
- The number of subjects who breakthrough any time during treatment and accompanying listing;
- The number of completers with final on-treatment HCV RNA < LLOQ who relapse within the SVR₄ window, SVR₁₂ window, or SVR₂₄ window and accompanying listing;
- The concordance between SVR₁₂ and SVR₂₄ will be assessed.

In the above analyses that use the number and percentage of responders, 2-sided 95% Wilson score confidence interval for a binomial proportion will be calculated.

Imputations for missing data will be performed as described in Section 6.3 for analyses of SVR, RVR, and EOTR, where a missing response will be imputed as a failure after performing the described imputation. All other endpoints will be presented using data as observed. For the change from baseline to each post-baseline time point in PT/INR, Fibrotest, and albumin, descriptive statistics will be calculated.

The number and percent of subjects who fail to suppress HCV RNA and received at least 6 weeks of treatment (active study drug duration ≥ 36 days) will be tabulated along with the subject numbers corresponding to the subjects who failed to suppress.

The number of subjects who breakthrough at any time during treatment and within each protocol-specified visit (defined in Table 2) will be summarized along with a corresponding listing displaying the subject numbers at the first occurrence of breakthrough.

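### A completer who misses the SVR12 window and is later found quantifiable fails SVR12 on a measured value, but is recorded as missing follow-up and removed from mITT-I-GT+VF

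*SAP*

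**What the plan says.** Four rules in the SAP meet here.

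- **Status (6.3).** If flanking imputation leaves the SVR window empty and "there is an HCV RNA value after the window, then it will be imputed into the SVR window". The SVR12 window is Study Drug End Days 57 to 126 (Table 3). There is no upper limit on how late the carried-back value may be.
- **Reason (10.1).** Reason 2 for SVR12 non-response is "Relapse (defined according to the Relapse₁₂ definition for subjects who complete treatment". Relapse12 needs confirmed HCV RNA at or above LLOQ "between end of treatment and 12 weeks after last actual dose of active study drug", that is, "up to and including the SVR₁₂ assessment time point". Reason 4, missing follow-up data, takes "any subject who completed study drug without data in the" SVR12 window who does not meet reasons 1 to 3.
- **Scope of imputation (10.7).** Imputation applies to SVR, RVR and EOTR. "All other endpoints will be presented using data as observed".
- **Use of the reason (10.6).** mITT-I-GT+VF excludes subjects who missed SVR12 "due to reasons other than on treatment virologic failure or relapse". Its stated purpose is to remove discordant genotypes and failures that have nothing to do with study drug.

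**The concern.** The SVR12 status uses the late sample, but the reason for failure ignores it. A subject who fails because virus was measured is then reported as having no follow-up data.

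The error runs one way. If the window is empty and the later value is below LLOQ, SAP 6.3 carries that value back and the subject is a responder, provided there was no earlier confirmed virus. So, among completers who miss the window and return with usable central-laboratory data, the ones left in reason 4 are those whose carried-back value was quantifiable. For them the label is wrong in substance.

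Three outputs are at stake. Relapse is undercounted in the table of SVR12 failure reasons. The mITT-I-GT+VF rate rises, because a virologic failure leaves its denominator. The report can also contradict itself, since the relapse-by-window table in SAP 10.7 would list the same subject as a relapse.

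**Working it through.** The plan states no figure on this point, so the first check is a trace of the rules.

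**Trace.** Take a completer (study drug duration at least 77 or 154 days, by assignment) who is below LLOQ at the Final Treatment Visit and PT Week 4. There is no central or local value on Days 57 to 126. A later value is at or above LLOQ, is either confirmed or the last available, and precedes any new HCV treatment.

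| Rule | Result |
|---|---|
| Flanking (6.3) | Not met: the succeeding value is quantifiable |
| Back-imputation (6.3) | Quantifiable value enters the window: SVR12 failure |
| Reason 1, on-treatment failure | No |
| Reason 2, Relapse12 | No: no observed quantifiable value by Day 126. The last-value rule waives confirmation, not the time limit |
| Reason 3, premature discontinuation | No: completer |
| Reason 4, missing | Yes |
| Relapse24; Relapse-late | No: they require SVR12 and SVR24 respectively |
| Relapse-overall | Yes |

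A first return at PT Week 52 gives the same result.

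**Who is not affected.** A subject already quantifiable at PT Week 4, with the next value also quantifiable, meets Relapse12. Non-completers go to reason 3. Documented re-infection goes to reason 5 by design. A local value in the window can be used to assess relapse (SAP 6.3).

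**SVR24 reasons.** If the later sample falls on Days 127 to 210 (the SVR24 window), the subject fails SVR24 with data in the window, meets none of reasons 1 to 5, and becomes Other. If it falls on Days 211 to 266, it is still inside the PT Week 24 visit window but outside the SVR24 window. On the observed-data reading the label is then Missing.

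**Effect per subject on mITT-I-GT+VF.** Inputs: N = 1650 (SAP 4.2) and 4% SVR12 failure (SAP 4.3), so 66 failures and 1584 responders. Assumptions: all are genotype 1, V of the 66 failures are virologic, and k of those V are mislabelled. The rate as written is 1584 / (1584 + V − k).

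| V | k = 0 (correct) | k = 1 | k = 3 |
|---|---|---|---|
| 22 | 98.63% | 98.69% | 98.81% |
| 33 | 97.96% | 98.02% | 98.14% |
| 44 | 97.30% | 97.36% | 97.48% |

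The shift is about 0.06 points per subject at every V. ITT-I SVR12 stays at 1584/1650 = 96.0%.

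**How many subjects.** The documents give no missed-window rate, so 1 to 5% is an assumption. Relapse rates come from Protocol 3.0:

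- Placebo-controlled, non-cirrhotic: (6 + 1)/(322 + 151) = 7/473 = 1.5% and (5 + 2)/(173 + 123) = 7/296 = 2.4%; 2% is used.
- Cirrhotic, 12 weeks: 12/208 = 5.8%; 6% is used.

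Low: 1650 × 2% × 1% = 0.3. Middle: 1650 × 2% × 5% = 1.7. High, with cirrhotics at their cap of about 400: (400 × 6% + 1250 × 2%) × 5% = (24 + 25) × 5% = 2.5.

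These counts assume that missing the window is unrelated to relapse and that everyone who misses it returns. They do not subtract relapses already evident at PT Week 4.

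**The case against.** **The carried-back value may be the SVR12 assessment.** If a value placed in the window counts as the SVR12 assessment, Relapse12 could be met and the subject would be a relapse. The SAP nowhere says so. Relapse is itself one of the endpoints in 10.7, and that section presents everything other than SVR, RVR and EOTR as observed. It is fair to add that the SVR12 reasons are defined in 10.1 and are not in the 10.7 list, so two programmers could read the rule differently. That is a reason to settle it in the text.

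**The label is literally true, and the timing is unknown.** There are no data in the window, and the relapse may have come after Week 12. A window-based reason table with later relapse reported separately is a defensible design. This stands as a caution on the fix, which is why a flag is needed. It does not justify removing the subject from an analysis meant to drop only failures unrelated to study drug.

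**Broader readings that the documents do not support.** A reader might infer that the relapse vanishes from all virologic-failure analyses. It does not: Relapse-overall (10.1), the relapse-by-window and anytime table and listing (10.7), and the resistance population (10.8) all keep the subject. A reader might also infer that the subject is a non-event in the regression on virologic failure (10.5). That section names no relapse definition, so the outcome is undetermined; the regression also looks for predictors and does not estimate a regimen effect. Finally, applying 6% relapse to all 1650 gives 1650 × 6% × 5% = 5 subjects. That uses the 12-week cirrhotic rate for everyone, although cirrhotics are capped at about 400 and genotype 1a cirrhotics are mainly assigned 24 weeks, where relapse was 1/172 = 0.6%.

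**Conclusion.** The mismatch is real and narrow. As written, a completer first quantifiable after Day 126 with an empty SVR12 window is an SVR12 failure on measured virus, is labelled as missing follow-up, and is excluded from mITT-I-GT+VF.

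The size is about 0.06 percentage points per subject in that one sensitivity analysis, always upward, with roughly 0 to 3 subjects expected. The count rests on the assumed 1 to 5% missed-window rate and on Phase 3 relapse rates carried over to this study. The per-subject shift rests on the planned N and the 4% failure assumption.

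ITT-I SVR12 and the SVR12 grouping in the primary Cox analysis are unaffected. This is a worthwhile clarification and does not threaten the study's conclusions.

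**What to change.** In SAP 10.1:

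1. Extend reason 2 for SVR12 non-response. A completer with HCV RNA below LLOQ at the Final Treatment Visit, whose SVR12 failure rests on a carried-back value at or above LLOQ that is confirmed or is the last available value, is classed as relapse unless re-infection is documented. Flag these subjects as first detected after the SVR12 window.
2. Restrict reason 4 to subjects with no HCV RNA value in or after the window. A single later quantifiable value that is not confirmed and is followed by one below LLOQ then falls to Other, in line with the existing example there.
3. Add the matching class to the SVR24 reasons.
4. State that mITT-I-GT+VF (10.6) and the virologic-failure regression (10.5) use this class.

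The cost is a few sentences and a small programming change, with no new data. The reported relapse count may rise slightly and may include some relapses that occurred after Week 12; the flag lets readers separate them.

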10.2 Handling of Multiplicity

No adjustment for multiple comparisons is used in this open-label long-term outcome study.

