### **5.3.2 Efficacy Variables**

#### **5.3.2.1 Primary Variable**

The primary endpoint is the incidence of all-cause death, liver-related death, liver decompensation, liver transplantation, hepatocellular carcinoma, and the composite of any of the above outcomes observed during the post-treatment period.

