## **8.2 Determination of Sample Size**

Assuming 4% of subjects do not achieve SVR12 and assuming the 5-year event rate of the composite clinical outcome is 20% in the non-SVR12 subjects, with a 75% reduction in SVR12 subjects (Hazard Ratio of 0.25), then based on two-sample log rank test (using EAST 6.0), a sample size of at least 2000 subjects enrolled in TOPAZ-I and TOPAZ-II provides greater than 80% power to reject the null hypothesis of no difference between SVR12 and non-SVR12 subjects in the rate of clinical outcome events. Power calculations were based on a dropout rate of up to 20%.

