4.4 Planned Analysis

The primary analysis to evaluate the effect of response to treatment on clinical outcomes, will occur at the final analysis after all subjects have completed the study or prematurely discontinued the study. An interim analysis to assess the percentage of subjects achieving SVR₁₂ will occur after all subjects have completed the Post-Treatment Week 12 Visit or prematurely discontinued the study. For both final and interim analyses, data will be locked after performing appropriate data cleaning. Data after the interim analysis will be added to a subsequent version of the database. SAS[®] (SAS Institute, Inc., Cary, NC) for the UNIX operating system will be used for all analyses. All statistical tests and all confidence intervals will be two-sided with an α level of 0.05.

All analyses will be conducted by statisticians and statistical programmers at AbbVie or the designee according to the methodologies specified in this SAP.

There is no intention of shortening the follow-up time of subjects based on efficacy findings from the interim analysis. The intention is to follow all subjects who receive study drug for 260 weeks following treatment. There will be no statistical adjustment employed due to this interim analysis.

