10.0 Efficacy Analysis

10.1 General Considerations

The primary efficacy analysis on clinical outcomes will be performed on all subjects in the ITT population as defined in Section 5.1. All other efficacy analyses will be performed on the ITT-I population.

Treatment effects will be evaluated based on a two-sided significance level of 0.05 (when rounded to three decimal places). The data from the ITT-I population will be presented in one column/row as it represents the labelled treatment.

Plasma HCV RNA levels will be determined for each sample collected by the central laboratory using the COBAS[®] AmpliPrep/COBAS[®] TaqMan[®] HCV Test, v2.0. For this assay, the lower limit of quantification (LLOQ) and the lower limit of detection (LLOD) is 15 IU/mL. HCV RNA results that are detectable but not quantifiable are reported as "< 15 IU/mL" and results that are not detectable are reported as "NON-DETECTED."

Assessment of Clinical Outcomes

Incidence of the following clinical outcome events will be collected during the 12/24 weeks of treatment and the 5-year (PT Week 260) Post-Treatment Period. Data will be adjudicated by an independent outcome committee and results will be reported in the "Clinical Outcome" eCRFs:

- All-cause death: Death due to any cause.
- Liver-related death: Death as the result of a liver-related cause.
- Liver decompensation: Development of any of the following conditions: ascites, hepatic encephalopathy, or variceal bleeding.
- Liver transplantation: any subject who had a liver transplantation.

- Hepatocellular carcinoma (HCC): development of HCC in any subject at any time during the study. HCC is defined by histologic confirmation or a > 1 cm mass lesion on cross-sectional imaging that meets the diagnostic criteria for HCC according to EASL guidelines.
- Composite of any of the above outcomes.

Definitions for HCV RNA Efficacy Endpoints

Note that a confirmed quantifiable post-treatment value is defined as two consecutive post-treatment HCV RNA measurements \geq LLOQ. During treatment, a confirmed quantifiable value is defined as any two consecutive HCV RNA values \geq LLOQ, either both during treatment or at the final treatment measurement and the next consecutive post-treatment measurement.

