10.3 Primary Efficacy Analysis

The primary efficacy analysis will be conducted among subjects in the ITT population as described in Section 5.1. HCV RNA values and SVR₁₂ will be imputed as described in Section 6.3.

The primary efficacy endpoint is to assess the effect of response to treatment (as assessed by SVR₁₂ status) on clinical outcomes by comparing the time to incidence of the following events between subjects who achieve SVR₁₂ and those who do not.

- All-cause death
- Liver-related death
- Liver decompensation
- Liver transplantation
- Hepatocellular carcinoma
- Composite of any of the above outcomes

For each of the six event types as listed above, a subject's time to event will be defined as the number of days from the first day of study drug to the day the subject experiences an event of interest. All events of interest will be included, regardless of whether the event occurred while the subject was still taking study drug or had previously discontinued study drug. However, events occurred after a subject started another treatment for HCV will be excluded and the subject will be censored at the time of starting the new HCV treatment. If the subject has not experienced an event of interest nor has the subject died (all-cause death), the subject's data will be censored at the date of the subject's last available assessment of clinical outcomes. All-cause death is a censoring event for liver-related death, liver decompensation, liver transplantation and hepatocellular carcinoma. For subjects with no post-baseline assessment, the subject's data will be censored on the first day of study drug. Time to the composite of clinical outcomes is the time to the first occurrence of any clinical outcome.

For each of the six event types, the distribution of time to event will be estimated for subjects who have achieved SVR₁₂ and those who haven't using Kaplan-Meier methodology and compared between the subjects who have achieved SVR₁₂ and those who haven't using the log-rank test.

For each of the six event types, the 1-, 2-, 3-, 4-, and 5-year event-free survival rate will be estimated using Kaplan-Meier methodology and a 95% confidence interval will be constructed separately for those who have achieved SVR₁₂ and those who haven't.

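### Six unranked outcomes form the primary endpoint, each tested at two-sided 0.05 without adjustment, while the sample size rests on a single test of the composite

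*SAP*

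**What the plan says.** - **Endpoint.** Protocol 5.3.2.1: "The primary endpoint is the incidence of all-cause death, liver-related death, liver decompensation, liver transplantation, hepatocellular carcinoma, and the composite". The Synopsis, Protocol 8.1.2.1 and SAP 10.3 carry the same six items. None ranks them or gives a success rule.
- **Analysis.** SAP 10.3 treats the six alike: "For each of the six event types as listed above, a subject's time to event will be defined". Each then gets three comparisons of SVR12 achievers with non-achievers: a log-rank test, a test of Kaplan-Meier estimates at Year 5, and a Cox model with baseline covariates. The Protocol (Synopsis and 8.1.2.1) names only the Cox model.
- **Alpha.** SAP 4.4: "All statistical tests and all confidence intervals will be two-sided with an α level of 0.05". SAP 10.1 repeats the 0.05 level for efficacy.
- **Multiplicity.** SAP 10.2: "No adjustment for multiple comparisons is used in this open-label long-term outcome study".
- **Sample size.** Protocol 8.2 and SAP 4.3 use the composite only, "assuming the 5-year event rate of the composite clinical outcome is 20" per cent in subjects without SVR12, with a hazard ratio of 0.25 and a two-sample log-rank test.

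**The concern.** The sample size section treats the composite as the primary test. The analysis section gives it no priority over the other five outcomes. These can disagree: the composite could miss significance while decompensation reaches it. The plan does not say what would be concluded then, and nothing in it stops a lone significant component being reported as a primary finding. Read that way, 0.05 is not the chance of a false primary claim, and the stated power covers only one of the six comparisons.

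The open-label, long-term design mentioned in SAP 10.2 does not change the error rate of six tests. Nor are the analyses purely descriptive: the sample size section powers rejection of a null hypothesis, and SAP 10.3 tests one for each event type.

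**Working it through.** **1. The plan's own power figure**

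Inputs (Protocol 8.2, SAP 4.3): N = 2000, 4% without SVR12 (80 v 1920), 5-year composite rate 20% without SVR12, hazard ratio 0.25, dropout up to 20%. Exponential event and dropout times over 5 years are my assumption.

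- Annual hazard without SVR12: −ln(0.80)/5 = 0.0446. With SVR12: 0.25 × 0.0446 = 0.0112, a 5-year rate of 1 − 0.8^0.25 = 5.4%. Dropout hazard: −ln(0.80)/5 = 0.0446.
- Probability of an observed event: λ/(λ+γ) × [1 − exp(−5(λ+γ))], where λ is the event hazard and γ the dropout hazard. This gives 0.180 without SVR12 and 0.0487 with it.
- Expected events: 80 × 0.180 + 1920 × 0.0487 = 14.4 + 93.5 = 107.9.
- Schoenfeld: z = √(107.9 × 0.04 × 0.96) × |ln 0.25| − 1.96 = 2.036 × 1.386 − 1.96 = 0.86, so power is 0.806. The formula needs 107 events for 80%.

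The stated power reproduces as one composite test at two-sided 0.05. Direct log-rank simulation gives about 0.98, so the formula is conservative with an allocation this uneven.

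**2. Chance of at least one p < 0.05 among six when SVR12 has no effect**

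- Independent tests: 1 − 0.95^6 = 0.265, or 5.3 × 0.05.
- Equicorrelated normal statistics: 0.241, 0.207, 0.164 and 0.108 at correlations 0.3, 0.5, 0.7 and 0.9. The last is 2.2 × 0.05.

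**3. Null simulations with the plan's structure**

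N = 2000, 80 without SVR12, 20% dropout, 5 years, nested outcomes, death censoring the non-fatal events, one log-rank test per outcome, 6000 trials per row. The rates are assumptions. HCC, decompensation and non-liver death are 5-year rates. The next column gives the annual hazards of liver death and transplantation after HCC or decompensation.

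| HCC / decompensation / non-liver death | Hazards | Any of six | Multiple of 0.05 | Composite alone |
|---|---|---|---|---|
| 2% / 2% / 2% (composite near the plan's overall 6%) | 0.10, 0.03 | 0.218 | 4.4 | 0.046 |
| 1% / 1% / 3% | 0.08, 0.02 | 0.232 | 4.6 | 0.047 |
| 7% / 8% / 6% | 0.12, 0.05 | 0.209 | 4.2 | 0.049 |
| 1% / 5% / 0.5% (strong overlap) | 0.5, 0.3 | 0.151 | 3.0 | 0.044 |
| 0.2% / 6% / 0.1% (very strong overlap) | 2, 2 | 0.157 | 3.1 | 0.045 |

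The plan's overall rate is 0.04 × 20% + 0.96 × 5.4% = 6.0%.

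A separate set of 3000 trials per scenario assumed 5-year rates for liver death, other death, decompensation, transplantation and HCC of 0.6/2.0/1.2/0.4/1.4% and 2/3/3/1/4%. Any-of-six log-rank rates were 0.230 and 0.206. With a single-covariate Cox Wald test they were 0.185 and 0.175. The composite alone gave 0.044 and 0.049. The SAP's fully adjusted Cox model was not simulated.

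**4. Why rare components matter with 4% in one group**

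Suppose four subjects in all have a transplant (an illustrative total). One of them in the non-SVR12 group gives z = (1 − 0.16)/√(4 × 0.04 × 0.96) = 2.14, p ≈ 0.03. Under the null, at least one of the four falls there with probability 1 − 0.96^4 = 0.15. With five events, one is no longer enough: z = 0.80/√(5 × 0.0384) = 1.83.

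**5. What is not counted**

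These figures use one test per outcome. In simulations with 80 non-SVR12 subjects, adding the Year-5 Kaplan-Meier test for all six outcomes raised the chance of any p < 0.05 to about 0.60 or more, because its variance estimate breaks down when that group has few or no events.

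**The case against.** The choice is disclosed. SAP 10.2 says plainly that nothing is adjusted, in a single-arm, non-randomised Phase 3b study. A reader might infer that the plan counts significance on any one outcome as a positive study. No section says so; the plan is silent, and the any-of-six rate depends on that reading. One could equally take the composite as the lead outcome, since it alone carries the sample size. That is a reasonable guess, but no section states it, and disclosing the lack of adjustment does not say which result decides.

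A reader might also infer a fixed fourfold inflation. The documents do not support one figure: they give no component rates or correlations, and the multiple falls to about 3 when the outcomes overlap strongly.

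Nor does the point show that the study is too small. The composite's stated power reproduces, and a Bonferroni split is not needed. At 0.05/6 = 0.0083 the Schoenfeld power would drop to about 0.57 (0.945 in direct simulation).

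Finally, SVR12 is a post-baseline, non-randomised grouping, so confounding can produce false differences that no multiplicity rule removes. That stands, and it limits what the fix can achieve.

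**Conclusion.** The concern holds as a mismatch between the sample size section and the analysis section. Alpha and power are stated for one composite test, but six outcomes share primary status without order or adjustment. If SVR12 affects none of them and any one significant result is read as primary, the false-claim rate is roughly 2 to 5 times 0.05. The central simulated log-rank values are 0.21 to 0.23, with about 0.15 under strong overlap and 0.265 under independence. The component rates behind the simulations are assumptions, and the count leaves out the choice among three tests per outcome. With one log-rank test of the composite alone, the simulated error stays near 0.05 (0.044 to 0.049) and the stated power applies.

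**What to change.** In Protocol 5.3.2.1 and 8.1.2.1 (and the Synopsis) and SAP 10.2 and 10.3:

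- Name time to first composite outcome as the single primary endpoint.
- Name one decisive test of it at two-sided 0.05. The Protocol names the Cox model, whereas the sample size uses the log-rank test; the sponsor should state which decides. The other two comparisons become supportive. If Cox is chosen, its covariates need fixing in advance, because SAP 10.3 leaves the list open.
- Make the five components secondary, reported as hazard ratios with 95% confidence intervals and no confirmatory claim.
- Replace the SAP 10.2 sentence to match.

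**Cost.** No added subjects or data, and the planned analyses stay. The stated power is unchanged if the log-rank test decides; if Cox decides, power should be restated for it. The sponsor can no longer call a lone significant component a primary result. The change needs a protocol amendment with ethics committee approval and, where local rules require it, regulatory approval (Protocol 9.1). TOPAZ-II needs matching wording, because its data are pooled in the primary analysis. Confounding between the SVR12 groups needs separate treatment.
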